5.4 Extension Analysis Population

Extension subjects are those who agree to continue study device use after 12 months, up to 2 additional years for a total maximum of 3 years.

5.5 Evaluable for Pregnancy Analysis Population

Evaluable for pregnancy (EP) analysis population will include only those safety subjects who underwent the study device placement successfully, and must meet requirements 1, 2 and 3 as follows. Subjects must also meet either requirement 4 or 5 to be EP.

The requirements are

1. between 18 to 35 years of age (inclusive) at enrolment;
2. at least one report of pregnancy status after being enrolled;
3. do not have pre-treatment pregnancy, which is defined as the estimated conception date being before the insertion date.

AND

4. have at least 1 cycle with intercourse and without any backup contraception or emergency contraception;

OR

5. became pregnant while study device LevoCept was in place.

Certain protocol deviations (PDs) are major in which they may affect the ability to assess the true effect of the trial device. Major protocol violations will be those reasonably considered to have had a material impact on the primary efficacy assessment. Subjects with major protocol violations will be excluded from EP analysis population.

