### **12.7 Emergency Contraception**

If the subject suspects the LevoCept has expelled, she should contact the study site immediately. The subject should be counselled to avoid intercourse until an exam can confirm expulsion. Emergency contraception may be administered, according to product labelling, if the subject suspects expulsion has occurred and an act of intercourse might be unprotected, and she does not want the risk of pregnancy. If the subject is subsequently found to have an *in-situ* IUD and desires to continue in the study, the cycle during which she used EC will not be included in the analysis unless the subject conceives. If the IUD is expelled, she will be exited from the study and followed for 6-8 weeks for occurrence of pregnancy.

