## **20.6 Primary Outcome**

The primary outcome measure is effectiveness and will be evaluated as absence of pregnancy during LevoCept use. Pregnancies judged to have occurred while a study device was in place (determined by ultrasound and medical assessments) will be included in the analysis of pregnancies.

For the primary evaluation of effectiveness, the Pearl index (and 95% confidence intervals) will be calculated in subjects aged 18-35 at the time of LevoCept placement through the date of LevoCept removal or pregnancy, excluding the following (unless the subject became pregnant in the cycle):

- Cycles where back-up contraception use was reported by the patient
- Cycles with no intercourse.
- Cycles in which emergency contraception was used

The Pearl Index is based on 28-day cycles and defined as the number of pregnancies per 100 woman-years (with one year comprising 13 28-day cycles). The cycle is defined as 28 days with the day of LevoCept placement as cycle 1

day 1. Pearl index will be summarized annually for each of the 3 years and cumulatively.

The EP population will be used for the primary evaluation of effectiveness.

Life table (Kaplan-Meier method) analyses will be used as further assessment of pregnancies. Pregnancy rate will also be summarized annually for each of the 3 years and cumulatively.

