4.1 Efficacy Variable

The primary outcome measure is effectiveness and will be evaluated as absence of pregnancy during study device use.

E-Diary data from the day of study placement to end of study/exit will collect the following information:

- 1) Menstrual and intermenstrual bleeding;
- 2) Vaginal intercourse;
- 3) Pain with intercourse;
- 4) Use of additional contraception;
- 5) Menstrual pain or cramping;
- 6) LevoCept expulsion

When data is still missing for a day after final attempt to have subject complete E-Diary, Vaginal intercourse, Pain with intercourse and Use of additional contraception will be collected for that specific missing day during monthly contact. The CRF collected data is used as a back-up. It is always preferred for the subject to complete the E-Diary data. If it occurs for a particular day that there is both subject data and CRF collected data, the subject data will take precedence and be used.

1. Pearl index

The primary efficacy variable is Pearl index. The Pearl index based on 28-day cycles and defined as the number of pregnancies per 100 woman-years (with one year comprising 13 28-day cycles). It will be calculated as:

$$\text{Pearl index} = \frac{N \times 1300}{L} = \frac{\text{Number of pregnancies} \times 1300}{\text{Number of woman-cycles of pregnancy at risk}}$$

Where n is the number of pregnancies, L is the number of woman-cycles of pregnancy at risk.

Only pregnancies judged to have occurred during study device use, or for which the estimated date of conception was within 7 days after study device removal or calculated date of expulsion are counted.

The number of woman-cycles of pregnancy at risk is the sum of the number of 28-day cycles for each subjects from the date of study device successful placement through the date of study device removal/expulsion or pregnancy, whichever comes earlier, excluding the following (unless the subject became pregnant in the cycle):

- Cycles where back-up contraception or emergency contraception use was reported by the subject;

- Cycles with no intercourse.

The cycle is defined as 28 days with the day of study device successful placement as cycle 1 day 1. The last cycle of pregnancy risk can be a partial cycle and the number of cycles can have one decimal place. The number of cycles (NC) of pregnancy risk for each subject will be calculated as:

$$NC = \frac{\min(\text{Date of removal/expulsion, Date of conception}) - \text{Date of placement}}{28}$$

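### SAP 5.5 requirement 5 is narrower than the SAP 4.1 pregnancy count, so a countable conception after early expulsion or removal can fall outside the primary population

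*SAP*

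**What the plan says.** **Numerator.** SAP 4.1 counts pregnancies that began while the woman was using the device, and it adds a second group: "or for which the estimated date of conception was within 7 days after study device removal or calculated date of expulsion are counted". It also removes cycles with back-up contraception, emergency contraception or no intercourse from the time at risk, but keeps such a cycle if the woman conceived in it.

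**Population.** SAP 5.5 first requires age 18 to 35, a pregnancy-status report after enrolment, and no conception before insertion. It then adds: "Subjects must also meet either requirement 4 or 5 to be EP". Requirement 4 is to "have at least 1 cycle with intercourse and without any backup contraception or emergency contraception". Requirement 5 is that she "became pregnant while study device LevoCept was in place". The footnotes to Table 14.1.5 and Listing 16.2.3.1 repeat the in-place condition.

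**Link between the two.** Protocol 20.6 states: "The EP population will be used for the primary evaluation of effectiveness". In the SAP, Table 14.2.1 (Pearl Index), Table 14.2.2 (pregnancy rate) and all the Kaplan-Meier figures are in EP only.

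**Protocol.** The synopsis includes the 7-day window in what it calls the per protocol analysis of pregnancies. Protocol 20.6 counts only pregnancies with a device in place, and Protocol 20.1 uses the same in-place condition for EP. SAP 8.2 lists two changes from the protocol, to the safety population and to the handling of pre-treatment pregnancies. It says nothing on this point.

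**The concern.** EP membership is settled before any pregnancy is counted. A woman outside EP contributes no event, whatever SAP 4.1 says about her conception. Requirement 5 evidently exists to admit failures that have no clean cycle, and SAP 4.1 keeps a pregnancy cycle despite back-up or emergency contraception for the same purpose. But requirement 5 stops at the moment the device leaves the uterus, while the numerator runs 7 days longer.

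The protocol itself creates ways to have no clean cycle. On expulsion, Protocol 12.7 says: "Emergency contraception may be administered, according to product labelling, if the subject suspects expulsion has occurred". Protocol 12.3.1 provides emergency contraception at some immediate removals. Protocol 4.1.1 has some women continue a hormonal method for 7 days after insertion, and the diary lists hormonal contraception as an additional method.

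The plan's own scenario has one pregnancy in the primary population, so each classification matters to the reported index. The mismatch can only remove pregnancies, so any error makes the device look better. Left open, the status of such a pregnancy would have to be argued after it was known.

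**Working it through.** **Step 1. The plan's own figure.** Inputs: 1 pregnancy, 2,015 cycles, index 0.6, 95% CI (0.1, 3.3) (SAP 3.2); multiplier 1300 (SAP 4.1).

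- Index = 1 × 1300 / 2015 = 0.645, which rounds to the stated 0.6.
- Exact Poisson CI: 0.0253 × 1300 / 2015 = 0.02 and 5.5716 × 1300 / 2015 = 3.59. A Poisson score interval gives 0.11 to 3.65. Neither is (0.1, 3.3).
- A score interval on 2,240 cycles, the all-ages target, gives 0.10 to 3.29. The stated interval may therefore rest on the all-ages count. That is an inference, and the point here does not depend on it.

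The SAP names no interval method. The exact Poisson intervals below are an assumption.

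**Step 2. Trace one woman.** She is aged 18 to 35, expels the device in cycle 1, has emergency contraception recorded in that cycle, and conceives within 7 days after the calculated expulsion date.

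| Rule | Result |
|---|---|
| SAP 4.1 numerator | Counts (7-day window) |
| SAP 5.5 requirements 1 to 3 | Met, given a reported pregnancy test |
| SAP 5.5 requirement 4 | Not met: her only cycle has emergency contraception, and this requirement has no waiver for a conception |
| SAP 5.5 requirement 5 | Not met: the device was no longer in place |
| EP | Out |
| Tables 14.2.1 and 14.2.2, Kaplan-Meier figures | Absent |

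The waiver in SAP 4.1 does not help. It decides which cycles count, not who is in EP.

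**Step 3. Who is exposed.** Requirements 4 and 5 are alternatives. A woman with even one earlier cycle with intercourse and no back-up or emergency contraception is in EP, and her post-removal or post-expulsion conception is counted. The loss is confined to women with no such cycle, mainly those whose device leaves in cycle 1. Two unclear points could widen that group: SAP 5.5 does not say whether a partial cycle satisfies requirement 4, and the Table 14.1.5 footnote asks for an e-diary cycle where SAP 5.5 asks only for a cycle.

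**Step 4. Effect of one lost pregnancy at 2,015 cycles.**

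| Pregnancies counted | Index | Assumed exact Poisson 95% CI |
|---|---|---|
| 0 | 0 | 0 to 2.38 (upper limit 3.689 × 1300 / 2015) |
| 1 | 0.65 | 0.02 to 3.59 |
| 2 | 1.29 | 0.16 to 4.66 |

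Losing the only pregnancy moves the result from the second row to the first. Losing one of two moves it from the third row to the second. Her own time at risk hardly matters: with one extra cycle, 1 × 1300 / 2016 = 0.6448 against 0.6452.

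**The case against.** The strongest reply is that this almost never happens. The plan assumes an average of 10 evaluable cycles per woman and 9.2% of cycles lost to no intercourse or back-up, so nearly all women enter EP through requirement 4. As a rough scale for first-cycle expulsion alone, using assumptions that are not in the documents, take 225 women, 1 to 3% expelling in cycle 1, 10 to 50% of those with disqualifying contraception, and 1 to 5% conceiving within 7 days. That gives between 225 × 0.01 × 0.10 × 0.01 = 0.002 and 225 × 0.03 × 0.50 × 0.05 = 0.17 expected cases. The rarity stands.

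It also stands that no decision turns on the result. There is no formal sample size calculation and no success threshold for the Pearl Index, and the intervals with and without the case overlap almost entirely.

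Nor would the case disappear from the report. Pregnancy tests, notifications and outcomes are listed for all enrolled subjects, Listing 16.2.3.1 shows which EP requirement failed, and SAP 5 requires exclusions to be documented with reasons. But a listing does not enter the estimate. The synopsis promises that all pregnancies will be counted in an intent-to-treat analysis, yet the SAP index has no such table.

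Finally, Protocol 20.1 and 20.6 agree with each other, since both use the in-place rule. A reader might infer that the protocol's Section 20 has the same internal mismatch; it does not. This does not rescue the SAP, which adopted the 7-day rule in 4.1 but kept the in-place population. Reading in place loosely as during use does not close the gap either, because SAP 4.1 lists the 7-day conceptions as a separate alternative.

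**Conclusion.** The point holds in a narrow form. Requirement 5 and the numerator disagree, and the disagreement can drop a pregnancy that the SAP says to count. It needs a conception within 7 days after removal or expulsion in a woman with no qualifying cycle. How often that occurs cannot be derived from the documents. The bias has one direction, in favour of the device. The shift from 0.65 to 0 assumes that the single planned pregnancy is this case, and its intervals assume an exact Poisson method.

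Two stronger readings are not supported. One is that conceptions after removal or expulsion are dropped in general; the alternative route through requirement 4 prevents that. The other is that the trial's conclusion hangs on this; the documents state no threshold that it could cross. It is an alignment error worth correcting because it is cheap to close and awkward to resolve once a case exists.

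**What to change.** In SAP 5.5, and in the footnotes to Table 14.1.5 and Listing 16.2.3.1, replace requirement 5 with: *had a pregnancy that counts under SAP Section 4.1, that is, conception while using the device or no more than 7 days after its removal or calculated expulsion*. Record this in SAP 8.2 as a departure from Protocol 20.1 and 20.6.

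Separately, reconcile Protocol 20.6 (in place only) with the protocol synopsis (7-day window). Protocol 20.1 should not be changed alone, because EP would then admit pregnancies that 20.6 does not count. The cross-reference to Section 4.1 should not be carried into the protocol, where Section 4.1 covers insertion timing.

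The cost is one line of SAP text, two footnotes and one entry in SAP 8.2, plus the protocol reconciliation if it is taken up. The reported index may be slightly less favourable.

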## **STATISTICAL METHODS**

### **Effectiveness Outcome**

The primary efficacy population will include all subjects aged 18-35 who had a study device successfully placed, provided at least 1 day of e-diary data, and were not pregnant before the IUD was placed.

Effectiveness will be evaluated as the absence of pregnancy during LevoCept use. Pregnancies judged to have occurred during study device use (determined by ultrasound and medical assessments), for which the estimated date of conception was within 7 days after study device removal or calculated date of expulsion, will be included in the per protocol analysis of pregnancies.

The Pearl Index (and 95% confidence intervals) will be calculated for cycles in subjects aged 18-35 at the time of study device placement through the date of LevoCept removal or pregnancy, excluding the following cycles (unless the subject became pregnant in the cycle):

- When back-up contraceptive or emergency contraceptive use was reported by the subject
- When the subject denied having any intercourse.

All pregnancies will be counted in the intent to treat analysis.

Life table analyses will be used as further assessment of pregnancies. Pregnancy rate will also be summarized annually for each of the 3 years and cumulatively.

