## **SAMPLE SIZE**

No formal sample size calculations were performed for the study. It is estimated that with 225 subjects enrolled with age 18-35, a 12-month Pearl Index of 0.6 (1 observed pregnancy), and 2,015 evaluable cycles, we will observe a 95% confidence interval for the 12-month Pearl Index of (0.1, 3.3).

2,015 evaluable cycles assumes that in the overall study:

- Each subject will average 10 evaluable cycles of LevoCept use
- 1% of subjects will not provide any e-diary data and will be excluded from the primary efficacy population
- Subjects will not have intercourse or will use backup contraception in 9.2% of cycles

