### **20.1 Analysis Populations**

The following analysis populations will be created:

All Enrolled: All subjects enrolled into the study.

Intent to Treat (ITT) / Safety: All enrolled subjects who underwent the study device placement procedure, regardless of whether the study device was successfully placed or not.

Evaluable for Pregnancy (EP):

Subjects must meet requirements 1 and 2 to be EP. Subjects must also meet either requirement 3 or requirement 4 to be EP.

1. between 18 to 35 years of age (inclusive) at enrollment
2. at least one report of pregnancy status after being enrolled  
AND
3. have at least 1 cycle of e-diary with intercourse and without any  
backup contraception or emergency contraception (EC)  
OR
4. became pregnant while LevoCept was in place.

Evaluable for Cycle Control (ECYC): all subjects Evaluable for Pregnancy with at least one cycle for which: A) a pregnancy did not occur; and B) there is bleeding related e-diary data.

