3.2 Study Sample Size

No formal sample size calculations were performed for the study. It is estimated that with 225 subjects enrolled with ages 18-35, a 12-month (13 cycles) Pearl Index of 0.6 (1 observed pregnancy), and 2,015 evaluable cycles, we will observe a 95% confidence interval (CI) for the 12-month Pearl Index of (0.1, 3.3).

4 Primary Efficacy and Safety Variables

For all change from baseline variables, baseline is defined as the last non-missing value on or before the day of study device successful placement. Change from baseline to post-baseline will be calculated as the post-baseline value minus the baseline value. If either the baseline or post-baseline value is missing for a particular variable, change from baseline will be missing.

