4. Bleeding and spotting

The total number of bleeding or spotting days for each subject at each cycle will be counted. The total number of bleeding and spotting days for each subject at each cycle will also be counted separately.

5. Discontinuation rate and reasons for discontinuation

Removal rates

The removal rate is defined as the percentage of the number of subjects with device removed among the total number of subjects enrolled in the study by that time-point.

Expulsion rates

The expulsion rate is defined as the percentage of the number of subjects with device expulsion among the total number of subjects enrolled in the study by that time-point.

Discontinuation rate

The discontinuation rate is defined as the percentage of the number of subjects discontinued study among the total number of subjects enrolled in the study by that time-point.

Reasons for discontinuation

The following reasons have been collected for exiting study:

- Adverse Event;
- Withdrew Consent;
- Protocol Violation;
- Lost to Follow-up;
- Investigator/Sponsor Decision;
- Pregnancy;
- Screen Failure;
- Other.

5 Analysis Populations

Data analyses will be based on the analysis populations defined below. Analysis populations, including exclusions based on major protocol deviations (PDs), will be reviewed and approved by the Sebelia and its designee. Excluded cases will be documented together with the reason for exclusion.

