12.1 Index of Tables

CONFIDENTIAL

ICH Heading	Table Number	Table Description
14.1		Demographics
	14.1.1	Subject Disposition (All Screened Subjects)
	14.1.2	Disposition by Site (All Enrolled Subjects)
	14.1.3	Summary of Subjects at Each Scheduled Study Visit (All Enrolled Subjects)
	14.1.4	Summary of Subjects with Protocol Deviations (All Enrolled Subjects)
	14.1.5	Analysis Populations (All Enrolled Subjects)
	14.1.6	Demographics and Baseline Characteristics (All Enrolled Subjects)
	14.1.7	Medical History (All Enrolled Subjects)
	14.1.8	Gynecological History (All Enrolled Subjects)
	14.1.9	Menstrual History (All Enrolled Subjects)
	14.1.10	Cervical Cytology (All Enrolled Subjects)
	14.1.11.1	Prior Medication (All Enrolled Subjects)
	14.1.11.2	Concomitant Medication (All Enrolled Subjects)
	14.1.11.3	Both Prior and Concomitant Medication (All Enrolled Subjects)
14.2		Efficacy
	14.2.1	Pearl Index (EP Population)
	14.2.2	Pregnancy Rate (EP Population)
14.3		Safety
14.3.1		Displays of Adverse Event
	14.3.1.1.1	Overall Summary of Treatment-Emergent Adverse Events (Safety Population)
	14.3.1.1.2	Overall Summary of Adverse Events (All Enrolled Subjects)
	14.3.1.2.1	Overall Summary of Treatment-Emergent Adverse Events by Severity and Relatedness to the Study Product (Safety Population)
	14.3.1.2.2	Overall Summary of Adverse Events by Severity and Relatedness to the Study Product (All Enrolled Subjects)
	14.3.1.3.1	Treatment-Emergent Adverse Events by System Organ Class and Preferred Term (Safety Population)
	14.3.1.3.2	Adverse Events by System Organ Class and Preferred Term (All Enrolled Subjects)
	14.3.1.4.1	Treatment-Emergent Serious Adverse Events by System Organ Class and Preferred Term (Safety Population)
	14.3.1.4.2	Serious Adverse Events by System Organ Class and Preferred Term (All Enrolled Subjects)
	14.3.1.5	Treatment-Emergent Adverse Events Leading to Study Device Removal (Safety Population)
	14.3.1.6	Treatment-Emergent Adverse Events as Primary Reason for Exiting Study (Safety Population)
	14.3.1.7	Treatment-Emergent Adverse Events Leading to Death (Safety Population)
	14.3.1.8	Treatment-Emergent Adverse Events by System Organ Class, Preferred Term and Severity (Safety Population)
	14.3.1.9	Treatment-Emergent Adverse Events by System Organ Class, Preferred Term and Relatedness to Study Device (Safety Population)

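### SAP 5.5 adds an undeclared, judgement-based exclusion of major protocol violators to the primary pregnancy population, and no all-pregnancy estimate is planned beside it

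*SAP*

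**What the plan says.** **Protocol.** Section 20.1 defines EP by four requirements: age 18 to 35, a pregnancy-status report after enrolment, and then one of two alternatives (an evaluable diary cycle, or pregnancy with the device in place). In its words, "Subjects must also meet either requirement 3 or requirement 4 to be EP". Protocol violations are not mentioned. Section 20.6 makes EP the population for the primary evaluation of effectiveness.

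**SAP.** Section 5.5 keeps these requirements and adds an exclusion of pre-treatment pregnancy, which section 8.2 declares. It then adds a further rule: "Subjects with major protocol violations will be excluded from EP analysis population". The only test for major is this: "Major protocol violations will be those reasonably considered to have had a material impact on the primary efficacy assessment". No categories of violation are listed. The opening of SAP section 5 says that the populations, "including exclusions based on major protocol deviations (PDs), will be reviewed and approved by" the sponsor and its designee, and that excluded cases will be documented with reasons.

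SAP 8.2 lists two departures from the protocol's populations. This is not one of them. The EP definitions in footnote [3] of Table 14.1.5 and footnote [1] of Listing 16.2.3.1 do not contain the rule either.

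**All-pregnancy analysis.** The statistical methods in the protocol synopsis state: "All pregnancies will be counted in the intent to treat analysis". In the SAP, Tables 14.2.1 and 14.2.2 and the three Kaplan-Meier figures are all labelled as EP.

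**Planning figure.** The protocol synopsis plans for "a 12-month Pearl Index of 0.6 (1 observed pregnancy), and 2,015 evaluable cycles". SAP 3.2 repeats the figure.

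**The concern.** The rule removes a whole subject, events included, on a judgement that another reader could not reproduce. Elsewhere both documents protect the numerator. A cycle with back-up contraception or no intercourse is dropped unless she conceived in it, and a woman who became pregnant with the device in place enters EP even without an evaluable cycle. The violation rule has no such protection, because SAP requirement 5 substitutes only for requirement 4.

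Pregnancies will be widely known during the study. Protocol 6.4 has them reviewed monthly, and protocol 20.8 has them communicated to all sites. In the text available, nothing separates that knowledge from the decision about who is a major violator, and no date fixes those decisions.

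Two things are at stake. First, the primary population is not reproducibly defined: a programmer working from SAP 5.5 and one working from the table footnotes could build different EP sets. Second, with about one event planned, a single decision can change the headline estimate, and no second estimate would show by how much.

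**Working it through.** **Inputs.** One pregnancy and 2,015 cycles at 12 months, ages 18-35 (protocol synopsis, sample size; SAP 3.2). Pearl Index (PI) = pregnancies x 1300 / cycles at risk (SAP 4.1). The synopsis assumes 10 cycles per subject, 1% of subjects without diary data, and 9.2% of cycles not evaluable.

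**Step 1: the plan's own figures.**
- Cycles: 225 x 0.99 x 10 x 0.908 = 2,023. With 222 whole subjects, 222 x 10 x 0.908 = 2,016. The plan's 2,015 is reproduced closely.
- Point estimate: 1 x 1300 / 2,015 = 0.645, which rounds to the stated 0.6.
- Interval: the plan states (0.1, 3.3). On 2,015 cycles, exact Poisson limits give (0.02, 3.59) and Wilson score limits on cycles give (0.11, 3.65). Neither matches. Wilson limits give (0.10, 3.28) on the all-age goal of 2,240 cycles, and (0.10, 3.30) on 225 x 0.99 x 10 = 2,227.5 cycles, so a larger denominator may have been used. This is a separate matter and the present point does not depend on it.

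**Step 2: effect of excluding one woman.** The available text names no interval method, so exact Poisson limits are assumed: lower = chi-square(0.025; 2x)/2 and upper = chi-square(0.975; 2x+2)/2, each multiplied by 1300/cycles. For x = 1 the count limits are 0.0253 and 5.572. For x = 0 the upper limit is 3.689.

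| Scenario | Pregnancies / cycles | PI | 95% CI |
|---|---|---|---|
| Planned case, pregnancy kept | 1 / 2,015 | 0.65 | 0.02 to 3.59 |
| That woman excluded, denominator held | 0 / 2,015 | 0 | 0 to 2.38 |
| That woman excluded with 10 cycles (assumed) | 0 / 2,005 | 0 | 0 to 2.39 |
| Two pregnancies, both kept | 2 / 2,015 | 1.29 | 0.16 to 4.66 |
| Two pregnancies, one woman and 10 cycles excluded | 1 / 2,005 | 0.65 | 0.02 to 3.61 |

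In the planned case the upper limit falls by (3.59 - 2.38) / 3.59 = 34%. With Wilson limits on cycles it falls from 3.65 to 2.47, or 32%, so the size does not hinge on the interval method.

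**Step 3: the other direction.** Excluding a non-pregnant violator with 10 cycles gives 1 x 1300 / 2,005 = 0.648 against 0.645, a rise of 0.003. The rule can move the estimate either way, but the two effects differ greatly in size.

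**Step 4: how likely the situation is.** At a true PI of 0.6, the expected count is 0.6 x 2,015 / 1300 = 0.93, so the Poisson probability of at least one pregnancy is 1 - 0.395 = 0.605. The documents give no violation rate, so the chance that a pregnant woman is also a major violator cannot be computed.

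**Step 5: where an excluded pregnancy would appear.** Listings 16.2.6.1, 16.2.6.4 and 16.2.6.5 (pregnancy tests, notification, outcome) cover all enrolled subjects. Listing 16.2.2.2 has a column for exclusion from EP beside each deviation. Table 14.1.1 counts pregnancy as a reason for discontinuation. No indexed output turns such a pregnancy into a rate.

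**The case against.** The best defence is that nothing is hidden. Exclusions are documented with reasons, Listing 16.2.2.2 provides for them, and every pregnancy in an enrolled woman is listed with its estimated conception date. In a single-arm study of about 250 women, a reader could find an excluded pregnancy and recompute the Pearl Index. This stands as far as it goes. A reader might infer that the pregnancy would vanish from the report, and that is not so. What is lost is a planned estimate with an interval.

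The all-pregnancy statement is also thin. It appears only in the synopsis, protocol 20.6 does not repeat it, and no denominator is given. The synopsis refers to a per-protocol analysis of pregnancies as well, and protocol section 20 leaves detail to the SAP. All of this is fair, and it calls for reconciliation rather than silence. SAP 6.2.7 and 6.2.8 are not in the text available and may say more. Even so, the table index, the figure index and the shells contain no such output.

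Three stronger readings should be resisted:
- **That exclusions will be decided after pregnancies are seen.** The documents do not say when they are decided. The table shells in the SAP (V2.0, 20 July 2018) carry redacted subject-specific notes, but these concern site transfers and failed placements. The gap is a missing safeguard, not evidence of misuse.
- **That the absence of ages 36-40 from the Pearl Index table is a defect.** The inclusion criteria take that group for safety only, and the Pearl Index is limited to 18-35 by design.
- **That a violation-excluded analysis should nevertheless keep every pregnant woman.** Dropping only non-pregnant violators would select on the outcome and bias the index upward.

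Finally, this is a Phase II study with no hypothesis test or success threshold, so no stated decision turns on 0 against 1 pregnancy. That limits the consequence but does not make the primary population reproducible.

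**Conclusion.** The point holds. SAP 5.5 adds to the primary population an exclusion that the protocol lacks, that SAP 8.2 does not declare and that the SAP's own EP footnotes contradict. It rests on a sponsor-approved judgement with no stated masking to pregnancy status and no freeze date. No planned efficacy output carries the synopsis statement that all pregnancies will be counted.

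The size is conditional: exactly one pregnancy by 12 months among ages 18-35, in a woman then classed as a major violator, with exact Poisson limits. The Pearl Index then moves from 0.65 (0.02 to 3.59) to 0 (0 to 2.38). Later years and the cumulative index may include more events, and one exclusion would then matter less. The conclusion that the rule is undefined and undeclared needs none of these assumptions.

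**What to change.** 1. Delete the major-violation exclusion from SAP 5.5, so that the primary EP population matches protocol 20.1 on this point and agrees with the footnotes to Table 14.1.5 and Listing 16.2.3.1.
2. If a violation-excluded analysis is wanted, run it only as a sensitivity analysis. List the violation categories in the SAP, and have them applied to all subjects by people without knowledge of pregnancy status, with the decisions frozen at a stated point before analysis.
3. Add one supportive table giving the Pearl Index and Kaplan-Meier rate with all pregnancies counted, to meet the synopsis statement. State its population, age range, denominator and pregnancy-counting window, since the protocol gives none of these for this analysis. The SAP's All Enrolled set (5.2) already has the same wording as the protocol's ITT definition and is a natural starting point.
4. Declare any remaining departure from the protocol in SAP 8.2.

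The cost is SAP wording and one or two extra tables from data already collected. The reported Pearl Index may be slightly less favourable.
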